4.5.3 Additional Safety Assessments

4.5.3.1 Electrocardiograms

ECGs are only required to be performed at screening to confirm the subject is eligible for the trial. Post-vaccination ECGs are performed only if clinically indicated; therefore, results from ECGs will be included only in subject level listings.

4.5.3.2 Vital Signs

Vital signs will be graded as in [Table 6](#) below, per the *Guidance for Industry: Toxicity Grading Scale for Healthy Adult and Adolescent Volunteers Enrolled in Preventative Vaccine Clinical Trials (FDA 2007)*.

Table 6 Vital Signs Grading

Vital Signs	Units	Mild (Grade 1)	Moderate (Grade 2)	Severe (Grade 3)	Life Threatening (Grade 4)
Fever	(°C)	38.0 – 38.4	38.5 – 38.9	39.0 – 40	> 40
	(°F)	100.4 – 101.1	101.2 – 102.0	102.1 – 104	> 104
Tachycardia	beats per minute	101 – 115	116 – 130	> 130	ER visit or hospitalization for arrhythmia
Bradycardia	beats per minute	50 – 54	45 – 49	< 45	ER visit or hospitalization for arrhythmia
Hypertension (systolic)	mm Hg	141 – 150	151 – 155	> 155	ER visit or hospitalization for malignant hypertension
Hypertension (diastolic)	mm Hg	91 – 95	96 – 100	> 100	ER visit or hospitalization for malignant hypertension
Hypotension (systolic)	mm Hg	85 – 89	80 – 84	< 80	ER visit or hospitalization for hypotensive shock

ER = emergency room; mm Hg = millimeters of mercury.

Note, the Grade 4 categories requiring a corresponding emergency room visit or hospitalization will not be included in this analysis, as they should be reported separately as SAEs. The frequency and percentage of subjects experiencing Fever, Tachycardia, Bradycardia, Hypertension (systolic and diastolic), and Hypotension (systolic) will be summarized for the Active Trial Period for any occurrence and by grade within vaccination group.

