	
restricted to abstinence (abstinence only acceptable if refraining from heterosexual intercourse during the entire period of 30 days prior to administration of the vaccine until 30 days after the vaccination), double barrier contraceptives, vasectomy, intrauterine contraceptive devices or licensed hormonal products.
 
 7. WOCBP must have a negative serum pregnancy test at SCR. 8. Negative human immunodeficiency virus antibody test (anti-HIV), negative hepatitis B surface antigen (HBsAG) and negative antibody to hepatitis C virus (HCV).
Exclusion Criteria	
 1. Group 1 only: History of COVID-19 infection or previous vaccination with a licensed or candidate SARS-CoV-2 vaccine, or positive qualitative test for SARS-CoV-2 antibodies at SCR. Groups 2 and 3 only: History of COVID-19 infection and subsequent receipt of more than one licensed or candidate SARS-CoV-2 vaccine. 2. Positive test for SARS-CoV-2 infection at SCR. 3. Pregnant or breastfeeding women. 4. Subject has an acute or chronic medical condition that, in the opinion of the investigator, would render the trial procedures unsafe or would interfere with the evaluation of the responses. 5. History of or active autoimmune disease. History of Guillain-Barré syndrome or Reye's syndrome. Persons with vitiligo or thyroid disease taking thyroid replacement are not excluded. 6. Known or suspected impairment of immunologic functions including, but not limited to, known immunodeficiency syndrome. 7. History of malignancy other than squamous cell or basal cell skin cancer, unless there has been surgical excision at least 6 months prior to SCR that is considered to have achieved cure. Subjects with history of skin cancer must not be vaccinated at the previous tumor site. 8. Laboratory parameters (such as complete blood count, serum biochemistry including aspartate aminotransferase [AST], alanine amino transferase [ALT], alkaline phosphokinase [AP], bilirubin, or creatinine values), pulse rate, blood pressure, or electrocardiogram (ECG) outside normal range at SCR and deemed clinically relevant by the investigator. 9. Clinically significant mental disorder not adequately controlled by medical treatment.

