9.18 Analyses of Safety

Other safety data will be summarized descriptively. AE data will be coded using the Medical Dictionary for Regulatory Activities (MedDRA). Solicited and unsolicited AEs will be summarized by system organ class, preferred term, and group. Solicited and unsolicited AEs that meet certain criteria, e.g., \geq Grade 2, \geq Grade 3, serious, related to vaccination, within 8 or 29 days after the first or the second vaccination will be summarized similarly.

The proportion of subjects testing positive for COVID-19 infection by timepoint and at any time post vaccination will be summarized by group.

Vital signs and safety laboratory data will focus on subject level changes, thus shifts from baseline will be summarized by group, and graphical presentations may be used.

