Appendix 3: Interpretation Support for Assessment of Screening ECGs

For a clearer and mutual understanding of inclusion criterion #8, the following provides clarifying explanations and examples pertaining to eligibility for enrollment.

Examples of subjects eligible for enrollment:

- Non-specific ST and T wave changes are not considered clinically significant and subject can be enrolled.
- Sinus bradycardia which does not require clinical intervention is not considered clinically significant and subject can be enrolled.
- Subjects who present with atrial disease which do not require clinical intervention, e.g., a pacemaker or drug treatment are allowed to be enrolled, as these can be considered not clinically significant. Examples are premature atrial contractions or ectopic atrial beats.
- Occasional premature ventricular contractions which do not require clinical intervention are not considered clinically significant and subject can be enrolled.
- First degree AV block or PR interval prolongations are also acceptable as long as they do not require clinical intervention, i.e., do not represent an indication for a pacemaker, and therefore the condition can be classified as not clinically significant.
- Right or left axis deviation which does not require clinical intervention is not considered clinically significant and subject can be enrolled.
- QTc prolongations <500 ms which do not require clinical intervention are not considered clinically significant and subject can be enrolled. QTc prolongations ≥ 500 ms which do not require clinical intervention should be discussed with the Medical Monitor before enrollment.

Examples of subjects NOT eligible for enrollment:

- Second or third degree atrioventricular block could represent significant heart disease and subject should not be enrolled.
- Incomplete left bundle branch blocks could represent significant heart disease and subject should not be enrolled.
- Significant ventricular disease represented by complete intraventricular conduction defects (complete left or right bundle branch block) must be considered clinically significant and subjects presenting with any such condition should not be enrolled. Left anterior or posterior intraventricular fascicular blocks or hemiblock could represent ventricular disease and subject should not be enrolled.
- ST elevation consistent with ischemia, subject should not be enrolled.
- Two premature ventricular contractions in a row, subject should not be enrolled.

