Per protocol, all visits are to occur within the specified window in the Trial Schedules ([Appendix 2](#) and [Appendix 3](#)). For the purpose of the primary estimand, rules for inclusion into the Immunogenicity Analysis Set will ensure immunogenicity samples taken too far out of window will not be included for analysis. For sensitivity analyses, immunogenicity samples taken out of window will be handled as described in Section [4.2.3.1](#).

In general, safety analyses will be performed for the Active Trial Period, accounting for any observations between the first vaccination and the EAP visit, inclusive of the EAP visit and any unscheduled visits during this period. In the event of early discontinuation from the Active Trial Period (i.e., EAP occurs prior to one month post last vaccination), safety results through 35 days (upper limit of the EAP visit window) post-last vaccination will be analyzed along with the Active Trial Period summaries. For Group 1, safety summaries will be performed by vaccination as well as for the overall Active Trial Period. Nominal visits will be used for the by-visit summaries, with the worst/highest toxicity grade value presented for the visit in the case of multiple reported observations.

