4.5.3.3 Laboratory Results

A list of laboratory parameters collected is included in Section 8.1.10 of the Clinical Trial Protocol. For the purpose of analysis, laboratory data will be converted to standard Système International d’Unités (SI) units during creation of the Study Data Tabulation Model (SDTM) datasets. The original laboratory values and units will also be stored in the SDTM datasets. Only the SI units will be used in tables and listings. SI units and conversions will be included in the SDTM documentation.

All measured laboratory values will be listed and summarized at each scheduled visit using descriptive statistics. Out of range laboratory values will be flagged as either “L” for below normal range or “H” for above normal range in listings. Clinically significant abnormal laboratory values are recorded as AEs and summarized along with the unsolicited AEs.

Toxicity will be graded based on the *Toxicity Grading Scale for Healthy Adult and Adolescent Volunteers Enrolled in Preventive Vaccine Clinical Trials* ([FDA 2007](#)). Grade 1 or Grade 2 toxicity is only graded according to this scale if the value is outside of the institutional normal range applicable for this trial.

Shift tables will be used to evaluate categorical changes in toxicity levels from baseline to each schedule time point, as well as to worst toxicity grade during the Active Trial Period, for laboratory parameters graded per the above toxicity scale.

For laboratory parameters not graded per the above toxicity scale, similar shift tables will be created based on the laboratory provided normal ranges (Low, Normal, High). Summary tables will be produced for the number of high and low laboratory values at each scheduled time point by laboratory category and parameter.

Any laboratory parameters which are not included in the protocol but reported by the laboratories (e.g., in order to define an AE) will be listed but not tabulated. Pregnancy test results will also be included only in listings.

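### SAP 4.5.3.2 counts any graded vital sign after vaccination without reference to baseline, although Protocol 9.18 plans shifts from baseline, and SAP 4.7 does not declare the change

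*SAP*

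**What the plan says.** Protocol 9.18 treats vital signs and laboratory data together: "Vital signs and safety laboratory data will focus on subject level changes, thus shifts from baseline will be summarized by group".

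The SAP splits them.

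- **Laboratory data (SAP 4.5.3.3):** "Shift tables will be used to evaluate categorical changes in toxicity levels from baseline to each schedule time point", and also to the worst grade in the Active Trial Period.
- **Vital signs (SAP 4.5.3.2):** "Vital signs will be graded as in" Table 6, which uses absolute cut-offs. The output is "The frequency and percentage of subjects experiencing Fever, Tachycardia, Bradycardia, Hypertension (systolic and diastolic), and Hypotension (systolic"), and these frequencies "will be summarized for the Active Trial Period for any occurrence and by grade within vaccination group". Baseline does not appear in this section.
- **Observations counted (SAP 4.1.3):** safety analyses cover the active period, with this scope: "accounting for any observations between the first vaccination and the EAP visit, inclusive of the EAP visit and any unscheduled visits during this period".

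SAP Section 1 sends changes to protocol-planned analyses to Section 4.7. That section lists two: the primary analysis limited to Groups 2 and 3, and an added 6-fold response threshold.

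On entry, exclusion criterion 8 (Protocol 1.3) removes a subject only when pulse or blood pressure is "outside normal range at SCR and deemed clinically relevant by the investigator". Protocol Appendix 3 adds: "Sinus bradycardia which does not require clinical intervention is not considered clinically significant and subject can be enrolled".

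**The concern.** A count of graded values after vaccination describes what happened after vaccination only if subjects start ungraded, or if the starting grade is taken into account. Neither holds here. The entry criteria let in subjects whose pulse or blood pressure already falls in a Table 6 grade, and the specified table ignores the starting value.

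The table therefore adds together two kinds of subject: those whose reading was the same before vaccination, and those whose reading moved. Its wording presents both as experiencing the condition in the Active Trial Period. The protocol's shift summary was the analysis that would have told them apart. It is missing for vital signs, and the SAP does not say so.

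**Working it through.** The plan gives no figure on this point to reproduce. The check is a comparison of texts, followed by an illustration of size.

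**1. Planned against specified**

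| | Protocol 9.18 | SAP |
|---|---|---|
| Laboratory data | shift from baseline, by group | shift tables (4.5.3.3) |
| Vital signs | shift from baseline, by group | any occurrence and by grade, no baseline (4.5.3.2) |
| Declared in SAP 4.7 | – | no |

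Both texts are current. Neither comes from an amendment summary.

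**2. Can a subject enter already graded?** Yes. Exclusion criterion 8 needs two conditions: out of range and judged clinically relevant. A value that meets only the first is admitted. Appendix 3 accepts sinus bradycardia that needs no intervention and states no lower limit for the rate. Two examples from Table 6:

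- Pulse 48 before and after vaccination lies in 45–49: Grade 2 bradycardia, no shift.
- Systolic pressure 152 before and after lies in 151–155: Grade 2 hypertension, no shift.

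If admitted, both are counted under SAP 4.5.3.2. In a shift table both stay on the diagonal (Grade 2 to Grade 2).

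**3. Is the shift computable?** Yes. Vital signs are scheduled at V1, and Protocol 4.4 requires examinations listed above the vaccination in the schedule to be done before it. SAP 4.1.1 defines baseline as the last measure before vaccination.

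**4. Size with stable values.** Let *p* be the share of subjects with a stable graded baseline value. The documents give no *p*, so 5% to 20% is an assumption. Subjects counted with no change = *p* × *n*:

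| *p* | Group 1 (*n* = 30) | Group 2 or 3 (*n* = 90) |
|---|---|---|
| 5% | 1.5 | 4.5 |
| 10% | 3 | 9 |
| 20% | 6 | 18 |

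**5. Size with visit-to-visit variation.** Systolic pressure was simulated with no vaccine effect, one V1 reading as baseline, and the worst of the scheduled later readings: three in Groups 2 and 3 (V2–V4), six in Group 1 (V2–V7). The mean, between-subject SD and within-subject SD are assumed. Percentages are of all subjects, for Groups 2 and 3:

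| Mean / SD between / SD within (mm Hg) | Graded at baseline | Any occurrence after | Worst grade not above baseline | Worst grade above baseline |
|---|---|---|---|---|
| 120 / 11 / 6 | 5.0% | 9.6% | 2.7% | 7.0% |
| 125 / 12 / 8 | 14.2% | 25.7% | 7.2% | 18.5% |
| 130 / 13 / 9 | 25.5% | 42.1% | 13.2% | 28.9% |

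The last two columns add up to any occurrence, apart from rounding. In these settings 2.7/9.6 = 28%, 7.2/25.7 = 28% and 13.2/42.1 = 31% of the counted subjects are no worse than at baseline. The other 70% or so moved up a grade through ordinary variation, and a shift table would still show them as worsened.

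For Group 1, with six readings, any occurrence is 13.4%, 33.9% and 52.3% in the same settings. The any-occurrence percentage thus depends on the number of visits even with no effect.

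**The case against.** The strongest reply is that the SAP is silent on shifts rather than opposed to them, and that other outputs fill the gap. SAP Section 1 says table shells are in a separate document. SAP 4.1.1 refers in general terms to shift-from-baseline analyses. SAP 4.1 plans vital-sign tables by time point and subject-level listings, and SAP 4.1.3 takes the worst grade per visit. New signs are also recorded as adverse events (Protocol 8.3 and 8.4). Vital signs are not a listed endpoint, and nothing is tested.

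Part of this stands. The gap may be an oversight rather than a decision, and within-subject changes can be traced in the listings. But by-visit tables show the distribution at each visit, not who moved, and listings are not the by-group summary that Protocol 9.18 promises. Absolute grading is not the defect, since Protocol 8.16 itself grades quantitative toxicities on the FDA scale. The missing baseline is.

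A reader might go further in four ways that the documents do not support:

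- **That the table would mostly show who was enrolled**, for example 14 of 90 (15.6%) against a true shift of 0 of 90. The 14 is a chosen value, and the zero assumes no within-subject variation. In the simulation most counted subjects did exceed their baseline grade.
- **That a change in an already abnormal subject cannot be seen.** The table is by grade, so a rise from Grade 1 to Grade 3 appears as Grade 3, though not marked as a change. The listings show it.
- **That a shift table would make the 100 µg and 50 µg groups comparable.** Groups 2 and 3 are filled in sequence without randomization. This affects every between-group safety table, and shifts do not cure it.
- **That the protocol requires counting only grades above baseline.** It asks for shifts to be summarized and sets no such counting rule.

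**Conclusion.** The discrepancy holds. Protocol 9.18 plans shifts from baseline for vital signs, SAP 4.5.3.2 specifies an any-occurrence count without baseline, and SAP 4.7 does not declare the difference. Given the entry criteria, stable pre-existing pulse and blood pressure values can be reported as experienced after vaccination, and the specified table cannot separate them from worsening.

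The documents do not allow the size to be fixed. Under the assumption that 5% to 20% of subjects have a stable graded baseline value, about 5 to 18 of 90 per seropositive group are affected. With visit-to-visit variation, under the assumed blood-pressure settings, about 3% to 13% of subjects are counted although no worse than at baseline. A larger share crosses a cut-off by variation alone, which a shift table does not remove.

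The issue concerns pulse and blood pressure; the entry criteria give little reason to expect stable fever at baseline. It is a defect in a descriptive safety output and does not touch the primary or secondary endpoints. It is worth correcting because the correction is simple.

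**What to change.** In SAP 4.5.3.2, add shift tables by group from baseline grade to each scheduled visit and to the worst post-vaccination grade in the Active Trial Period. Cover pulse and blood pressure, and temperature for completeness, in the form SAP 4.5.3.3 uses for laboratory values.

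Keep the any-occurrence table only if its title or footnote says that it includes values already present at baseline, or add a row for subjects whose worst grade exceeds their baseline grade. That row is an addition to what the protocol asks for. A footnote should give the number of scheduled readings (six in Group 1, three in Groups 2 and 3). Record any departure from Protocol 9.18 that remains, with the reason, in SAP 4.7.

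The cost is a few lines of SAP text and reuse of the laboratory shift-table program. The pre-vaccination readings are already scheduled. Under SAP 4.1.1, subjects without a baseline value drop out of the shift tables, so the tables should state how many there are.

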4.5.3.3 Laboratory Results

A list of laboratory parameters collected is included in Section 8.1.10 of the Clinical Trial Protocol. For the purpose of analysis, laboratory data will be converted to standard Système International d’Unités (SI) units during creation of the Study Data Tabulation Model (SDTM) datasets. The original laboratory values and units will also be stored in the SDTM datasets. Only the SI units will be used in tables and listings. SI units and conversions will be included in the SDTM documentation.

All measured laboratory values will be listed and summarized at each scheduled visit using descriptive statistics. Out of range laboratory values will be flagged as either “L” for below normal range or “H” for above normal range in listings. Clinically significant abnormal laboratory values are recorded as AEs and summarized along with the unsolicited AEs.

Toxicity will be graded based on the *Toxicity Grading Scale for Healthy Adult and Adolescent Volunteers Enrolled in Preventive Vaccine Clinical Trials* ([FDA 2007](#)). Grade 1 or Grade 2 toxicity is only graded according to this scale if the value is outside of the institutional normal range applicable for this trial.

Shift tables will be used to evaluate categorical changes in toxicity levels from baseline to each schedule time point, as well as to worst toxicity grade during the Active Trial Period, for laboratory parameters graded per the above toxicity scale.

For laboratory parameters not graded per the above toxicity scale, similar shift tables will be created based on the laboratory provided normal ranges (Low, Normal, High). Summary tables will be produced for the number of high and low laboratory values at each scheduled time point by laboratory category and parameter.

Any laboratory parameters which are not included in the protocol but reported by the laboratories (e.g., in order to define an AE) will be listed but not tabulated. Pregnancy test results will also be included only in listings.

4.5.3.4 SARS-CoV-2 Infection Results via PCR

The frequency and percentage of subjects testing positive for COVID-19 infection by visit, any infection prior to 2 weeks post-last vaccination, any infection after the 2 weeks post-last vaccination time point, and any infection post vaccination overall will be summarized by group. As collection may occur during unscheduled visits, frequencies and percentages will include all subjects who tested positive between the prior visit through the summarized visit.

4.5.3.5 Physical Examinations

The performance of physical examinations will be listed. Findings upon physical examination will be added to the Medical History case report form if they started prior to the signing of the ICF, and to the AE case report form page if starting afterward. Findings occurring after the signing of the ICF, but pre-vaccination will be categorized as baseline signs and symptoms, and post-vaccination events through the end of the Active Trial Period visit will be considered part of the Active Trial Period. Findings occurring after the Active Trial Period will be considered FU period AEs and only included in AE listings.

4.5.4 Subgroup Analyses

No additional subgroup analyses will be performed for safety endpoints.

4.6 Interim Analyses

Description of the run-in phase of the trial is included in Section 1.2. In order to inform the phase 3 trial, a primary analysis of immunogenicity and safety will be performed once all Group 2 and 3 subjects have completed the end of the active phase visit or withdrawn early from the trial, and at least the neutralizing antibody testing results supporting the primary endpoint are available. Trial data will be cleaned through the end of the Active Trial Period visit for these subjects, and a data review meeting will be conducted to review the key trial data for the primary analysis and determine the subjects to be excluded from the Immunogenicity Analysis Set.

The primary analysis will include both the primary and secondary estimand analyses, as well as the available safety, demographics, and disposition data through the end of the Active Trial Period for Groups 2 and 3. In addition, the total antibody data and neutralizing antibody titers against various variant strains at 2 weeks after last vaccination will be provided, if available.

The results of the primary analyses from the primary and secondary estimand analyses are not expected to change for later reporting, nor is statistical hypothesis testing to be performed. Therefore, the analyses for the primary estimand for Groups 2 and 3 performed at this time will be considered “final” for the purposes of this trial and no adjustments for multiple reviews of the data are required.

The final analysis for the trial will occur once all subjects have completed the follow up visits or withdrawn early from the trial and the database has been locked. Group 1, follow-up, and safety data through the end of the trial, as well as additional immunogenicity and SARS-CoV-2 infection testing performed at 3 months for all groups, as well as 6 months, 1 year, and 2 years for Groups 2 and 3 subjects will be reported in this analysis as an appendix to the primary analysis. These data will be in addition to the already reported trial results rather than a “re-analysis” of already reported endpoints. Although unlikely, any changes in the data or planned analyses from the primary analysis will be fully documented.

